3. ENDPOINTS AND BASELINE VARIABLES: DEFINITIONS AND CONVENTIONS

3.1. Primary Endpoint(s)

Primary Study Cohort - Stage 1:

- Local reactions within 14 days after Vaccination 1.
- Systemic events within 14 days after Vaccination 1.
- AEs within 1 month after Vaccination 1.
- MAEs and SAEs through 12 months after Vaccination 1 (from Visit 1 through Visit 5).

3.1.1. Local Reactions

The local reactions reported in the e-diary are redness, swelling, and pain at the injection site, from Day 1 through Day 14 after each vaccination, where Day 1 is the day of vaccination. This section describes derivations with details for the assessment of local reactions: any presence, maximum severity, duration, and onset day of local reactions, in addition to presence of severe local reactions on each day.

3.1.1.1. Presence of Local Reactions

For the summary of the presence (yes or no) of a local reaction during the interval from Day 1 through Day 14 after each vaccination, where Day 1 is the day of vaccination, the following 2 variables are required in order to compute the proportions:

1. Presence (yes or no) of each local reaction on any day (Day 1 through Day 14).

The derivation is described in Table 2.

Table 2. Derived Variables for Each Local Reaction

Variable ^a	Yes (1)	No (0)	Missing (.)
Any day (Days 1-14)	Subject reports the reaction as “yes” on any day (Days 1-14).	Subject reports the reaction as “no” on all 14 days or as a combination of “no” and “missing” on all 14 days.	Subject reports the reaction as “missing” on all 14 days.

a. The variable will be defined for each of the 3 local reactions.

2. Presence (yes or no) of any local reaction on any day (Day 1 through Day 14).

For any local reaction on any day, a similar definition can be applied as given in [Table 3](#).

Table 3. Derived Variables for Any Local Reaction

Variable	Yes (1)	No (0)	Missing (.)
Any day (Days 1-14)	Subject reports any local reaction as “yes” on any day (Days 1-14).	Subject reports the reaction as “no” on all 14 days or as a combination of “no” and “missing” on all 14 days for all 3 local reactions.	Subject reports all local reactions as “missing” on all 14 days.

3.1.1.2. Maximum Severity of Local Reactions

The grading of local reactions is listed in Table 4.

Table 4. Grading Scale for Local Reactions

	Mild Grade 1	Moderate Grade 2	Severe Grade 3	Grade 4 ^a
Redness	2.5 cm to 5.0 cm (5 to 10 measuring device units)	>5.0 cm to 10.0 cm (11 to 20 measuring device units)	>10 cm (>20 measuring device units)	Necrosis or exfoliative dermatitis
Swelling	2.5 cm to 5.0 cm (5 to 10 measuring device units)	>5.0 cm to 10.0 cm (11 to 20 measuring device units)	>10 cm (>20 measuring device units)	Necrosis
Pain (at the injection site)	Does not interfere with activity	Interferes with activity	Prevents daily activity	Emergency room visit or hospitalization for severe pain at the injection site

- a. Grade 4 assessment should be made by the investigator using the AE severity grading scale. The assessment will be collected on the AE case report form and thus not reported from the e-diary.

The following 2 variables are required in order to compute the proportions of subjects reporting maximum severity:

1. Maximum severity of each local reaction on any day (Day 1 through Day 14).

The maximum severity (highest grading) of each local reaction within 14 days after vaccination will be derived. The maximum severity will be derived as follows:

- = “Missing,” if values are missing for all days (Days 1-14);
- = 0, if the subject reports all reactions as “no” or a combination of “missing” and “no” for all days (Days 1-14);
- = Highest grade (maximum severity) within 14 days after vaccination, if the answer is not “no” for at least 1 day.

2. Maximum severity of any local reaction on any day (Day 1 through Day 14).

The maximum severity for any local reaction will be derived as follows:

- = “Missing,” if values are missing for all days (Days 1-14) across all 3 local reactions;
- = 0, if the subject reports all reactions as “no” or a combination of “missing” and “no” for all days (Days 1-14) for any individual location reaction;
- = Highest grade (maximum severity) within 14 days after vaccination, if the answer is not “no” for at least 1 day for at least 1 local reaction.

3.1.1.3. Duration of Each Local Reaction

The duration of each local reaction will be calculated in days as (resolution date of reaction – start date of reaction + 1). Resolution of the event is the last day on which the event is recorded in the e-diary or the date the event ends (according to the grading scale definitions in Table 4) if it is unresolved during the subject diary recording period (end date collected on the case report form [CRF]), unless chronicity is established. For this multiple vaccination study, the date the reaction ended for one vaccination should not be after the beginning of the next vaccination. If there is no known end date, the duration will be considered unknown and set to “missing.” Subjects with no reported reaction (including redness and swelling of less than 2.5 cm [5 measuring device units] per Table 4) have no duration.

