3.1.1.4. Onset Day of Each Local Reaction

The onset day of each local reaction will be derived. Onset day is defined as the first day of reporting any severity.

For the onset day of each local reaction, if a subject reports changes in severity of the local reaction, only the first day of reporting that specific local reaction will be counted.

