3.1.2. Systemic Events

Systemic events, including fever, fatigue, headache, vomiting, nausea, diarrhea, muscle pain, and joint pain, are reported via e-diary from Day 1 through Day 14 after each vaccination, where Day 1 is the day of vaccination. The derivations below for systemic events will be handled similarly to the way local reactions are handled for presence, severity level, duration, onset day, and severe systemic events on each day.

1. Presence (yes or no) of each systemic event on any day (Day 1 through Day 14).
2. Presence (yes or no) of any systemic event on any day (Day 1 through Day 14).
3. Maximum severity of each systemic event on any day (Day 1 through Day 14).
4. Maximum severity of any systemic event on any day (Day 1 through Day 14).
5. Duration of each systemic event.
6. Onset day of each systemic event.
7. Presence (yes or no) of any severe local reaction on each of the 14 days.

The systemic events gradings are provided in Table 6.

Table 6. Grading Scale for Systemic Events

	Mild Grade 1	Moderate Grade 2	Severe Grade 3	Grade 4^a
Fatigue (= tiredness in diaries)	Does not interfere with activity	Some interference with activity	Prevents daily routine activity	Emergency room visit or hospitalization for severe fatigue
Headache	Does not interfere with activity	Some interference with activity	Prevents daily routine activity	Emergency room visit or hospitalization for severe headache
Vomiting	1 to 2 times in 24 hours	>2 times in 24 hours	Requires intravenous hydration	Emergency room visit or hospitalization for severe vomiting
Nausea	Does not interfere with activity	Some interference with activity	Prevents daily routine activity	Emergency room visit or hospitalization for severe nausea
Diarrhea	2 to 3 loose stools in 24 hours	4 to 5 loose stools in 24 hours	6 or more loose stools in 24 hours	Emergency room visit or hospitalization for severe diarrhea

Table 6. Grading Scale for Systemic Events

	Mild Grade 1	Moderate Grade 2	Severe Grade 3	Grade 4^a
Muscle pain	Does not interfere with activity	Some interference with activity	Prevents daily routine activity	Emergency room visit or hospitalization for severe muscle pain
Joint pain	Does not interfere with activity	Some interference with activity	Prevents daily routine activity	Emergency room visit or hospitalization for severe joint pain

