3.1.3. Use of Antipyretic/Pain Medication

Antipyretic/pain medications used to treat symptoms are recorded in the e-diary. This variable will be presented along with systemic events summary, but not counted as a systemic event. The following variables will be derived:

1. Use of antipyretic/pain medication on “any day (Days 1-14)” after vaccination.
2. Duration of use of antipyretic/pain medication after vaccination.
3. Onset day of antipyretic/pain medication use after vaccination.

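### SAP duration is the interval from first to last recorded day, so symptom-free days between separate episodes count as reaction days; relabel it and add a count of days with the event

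*SAP*

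**What the plan says.** SAP 3.1.1.3 sets the duration of a local reaction, in days, to resolution date minus start date plus 1. On the end point it says "Resolution of the event is the last day on which the event is recorded in the e-diary"; if the event is still unresolved when the diary closes, the end date collected on the CRF is used. SAP 3.1.1.4 fixes the start: "Onset day is defined as the first day of reporting any severity". If severity changes, "only the first day of reporting that specific local reaction will be counted".

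The diary runs "from Day 1 through Day 14 after each vaccination, where Day 1 is the day of vaccination" (SAP 3.1.1). Section 3.1.1.3 has rules for events unresolved at diary end, chronic events, overlap with the next vaccination, unknown end dates, and redness or swelling below 2.5 cm. It has none for days answered 'no' between two recorded days.

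SAP 3.1.2 carries the derivation over to systemic events, which are "handled similarly to the way local reactions are handled for presence, severity level, duration, onset day". SAP 3.1.3 lists "Duration of use of antipyretic/pain medication after vaccination" without a formula of its own, and 6.1.3 says medication use is analysed like systemic events.

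Duration is tabulated by vaccine group as n, mean, median, SD, minimum and maximum, under the additional summaries in SAP 6.1.1.2 and 6.1.2.2. The primary analyses in 6.1.1.1 and 6.1.2.1 are proportions by maximum severity.

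**The concern.** The table rows will be labelled as the duration of each reaction or event, and a reader will take a value of 12 days to mean that the symptom lasted 12 days. Under the rule it may mean two days of headache after vaccination and one unrelated headache on Day 12.

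Fatigue, headache, nausea, muscle pain, joint pain and analgesic use all occur without vaccination in adults aged 65 to 85, so isolated later days are foreseeable. Redness, swelling and pain at the left-arm injection site are much less likely to recur for unrelated reasons.

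The stake is limited but real. The primary objective is to describe safety and tolerability, and interim results feed the choice of dose, formulation and schedule (Protocol 9.4, SAP 7.2). A mean or maximum that mixes reaction days with symptom-free days is a poor description of tolerability, especially in groups of about 31 (Protocol Table 4).

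**Working it through.** The plan states no figure for duration, recurrence or gap days, so there is nothing to reproduce. The check has four steps.

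**1. The rule on example diaries.** Span = last recorded day − first recorded day + 1.

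| Days recorded | Span by the rule | Days present | Excess |
|---|---|---|---|
| 2, 3, 4 | 4 − 2 + 1 = 3 | 3 | 0 |
| 2, 3, 9 | 9 − 2 + 1 = 8 | 3 | 5 |
| 1, 2, 3, 8, 9 | 9 − 1 + 1 = 9 | 5 | 4 |
| 1, 14 | 14 − 1 + 1 = 14 | 2 | 12 |

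The excess is zero for a continuous event and at most 12 days within the diary.

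**2. Possible size.** All rates here are assumptions. Complete 14-day diaries were simulated with an unrelated symptom on each day with probability 1%, 3% or 5%, independently and equally in everyone. A Day 1–2 event was added in 40% of vaccine subjects and in no placebo subjects. Means are among subjects with the event.

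| Background per day | Vaccine: span / days present | Placebo: span / days present | Vaccine subjects with a gap |
|---|---|---|---|
| 1% | 2.53 / 1.95 | 1.34 / 1.07 | 10% |
| 3% | 3.38 / 1.97 | 2.00 / 1.21 | 24% |
| 5% | 4.12 / 2.06 | 2.65 / 1.37 | 36% |

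At 3% the vaccine-arm SD is 3.5 days by span and 0.8 by days present. The vaccine median is 2 days either way. In an arm of 31, the tabulated maximum is 10 days or more with probability 0.47, 0.87 and 0.97 at the three rates. By days present this did not occur in 20,000 simulated arms per rate.

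**3. Direction between arms.** Excess = mean span − mean days present.

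- In the model above at 3%, the excess is 3.38 − 1.97 = 1.41 for vaccine and 2.00 − 1.21 = 0.79 for placebo.
- In the Primary Study Cohort, placebo subjects also receive SIIV at Visit 1 (Protocol Table 4 and 5.5). If SIIV causes a Day 1–2 event in 20% or 30% of them (assumed), the placebo excess rises to about 1.2 or 1.3, close to the vaccine value.
- If background symptoms are confined to 15% of subjects at 20% per day (assumed), placebo is 7.29 by span against 2.93 days present, an excess of 4.36. Vaccine is 3.95 against 2.46, an excess of 1.49. The order reverses, and the placebo median also moves (8 by span, 3 by days present).

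**4. Missing diary days.** For a continuous 4-day reaction with 10% or 20% of days missing at random (assumed) and no background symptoms, the day count averages 3.6 or 3.2 days and the span 3.8 or 3.5. Both fall short of 4, the count more so.

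**The case against.** The strongest defence is that the SAP's start, resolution and formula are explicit and agree with one another, and that time from onset to last resolution is a legitimate quantity. That stands: the span is worth keeping. It does not justify presenting the span, unqualified, as how long the event was present. The programming rules are in a separate document that was not available, but SAP 2 says they are based on the methods in the SAP, and the SAP specifies the span.

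It is also fair that duration is not a protocol primary endpoint, that everything is descriptive (SAP 5.1.2), that the median sits beside the mean, and that no between-group difference in duration is planned. These facts hold the point to minor. For medication use the span is inferred by reference and not written out. Replacing the span with a day count would also bring its own bias, because the e-diary accepts entries only in a fixed time window (Protocol 7.3.1) and missed days are foreseen (SAP 3.1.1.1).

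A reader might go further and infer that the rule inflates durations more in vaccine arms than in placebo, because an early vaccine reaction anchors the span at Day 1. The documents do not support this. They give no recurrence data by arm, SIIV can anchor the span in Primary Study Cohort placebo subjects too, and clustered background symptoms reverse the order.

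**Conclusion.** The point holds as a minor one. The written rule counts symptom-free days between separate episodes, so the mean, SD and maximum can overstate how long an event was present, mainly for systemic events and analgesic use. Whether and by how much they will do so depends on recurrence, which the documents do not quantify. With no recurrence the excess is nil. With an assumed background of 1% to 5% per day and a Day 1–2 event in 40% of vaccinees, the vaccine-arm mean is about 0.6 to 2.1 days too long as a measure of days present (2.53 − 1.95 = 0.58; 4.12 − 2.06 = 2.06). The effect may differ between arms, but its direction cannot be stated in advance. The primary proportions by maximum severity do not change.

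**What to change.** In SAP 3.1.1.3, and by reference in 3.1.2 and 3.1.3:

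- Keep the span, but label it 'interval from first to last day'.
- Add a row for the number of e-diary days on which the event is reported at Grade 1 or higher. For fever, count days at or above 38.0°C; for medication, count days of use. If the event is ongoing at diary end, add the further days to the CRF stop date.
- Report the number of missing diary days within the span, so that the possible undercount in the new row can be seen.
- State in 3.1.3 that the same two quantities apply to medication use.

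The daily entries are already collected, so the cost is one SAP sentence, a small programming change and an extra table row. Keeping the span preserves comparability with any study that reports it.

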- The investigator or an authorized designee completes the CRFs and an unblinded dispenser/administrator updates the investigational product accountability records.
- The investigator or appropriately qualified designee reviews the e-diary data online following vaccination to evaluate subject compliance and as part of the ongoing safety review. Daily review is optimal during the active diary period.

6.1.2. Primary Study Cohort - Stage 1, Visit 2: 1-Week Follow-up Visit (6-8 Days After Visit 1) (*applicable to consenting PBMC subjects at PBMC collection sites only*)

- Review the subject's e-diary data.
- Record nonstudy vaccinations as described in [Section 5.8.4](#).

- Confirm understanding of and compliance with protocol requirements for contraception (male subjects only).
- Collect a blood sample of approximately 50 mL for antibody assessment.
- Collect a blood sample of approximately 50 mL for cellular assays.
- Record AEs as described in [Section 8](#).
- Ask the subject to contact the site staff or investigator if a medically attended event (eg, doctor's visit, emergency room visit) or hospitalization occurs.
- Schedule an appointment for the subject to return for the next study visit.
- Complete the source documents.
- The investigator or an authorized designee completes the CRFs.

6.1.3. Primary Study Cohort - Stage 1, Visit 2: 1-Month Follow-up Visit (28-35 Days After Visit 1) (*applicable to all subjects*)

- Ensure that the subject meets none of the subject withdrawal criteria as described in [Section 6.5](#).
- Review the subject's e-diary data and collect the e-diary. Collect stop dates of any e-diary events ongoing on the last day that the e-diary was completed and record stop dates in the CRF if required.
- Confirm understanding of and compliance with protocol requirements for contraception (male subjects only).
- Collect a blood sample of approximately 50 mL for antibody assessment.
- Collect a blood sample of approximately 50 mL for cellular assays (from consenting PBMC subjects at PBMC collection sites only).
- Record nonstudy vaccinations as described in [Section 5.8.4](#).
- Record AEs as described in [Section 8](#).
- Complete the source documents.
- The investigator or an authorized designee completes the CRFs.
- Ask the subject to contact the site staff or investigator if a medically attended event (eg, doctor's visit, emergency room visit) or hospitalization occurs.

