7.3.1. Subject Electronic Diary

The subject will be asked to monitor and record local reactions (left arm), systemic events, fever, and antipyretics/pain medication used to treat symptoms, each evening for 14 days following each vaccination visit (Day 1 through Day 14, where Day 1 is the day of vaccination). The e-diary allows recording of these assessments only within a fixed time window, thus providing the accurate representation of the subject's experience at that time. Data on local reactions, systemic events, and antipyretics/pain medication used to treat symptoms recorded in the e-diary will be transferred electronically to the e-diary vendor, where they will be available for review by investigators, their qualified designees, and sponsor staff at all times via an internet-based portal. At intervals agreed to by the vendor and Pfizer, these data will be transferred electronically to Pfizer for analysis and reporting. These data do not need to be recorded by the investigator in the CRF. However, if a subject withdraws because of prompted events recorded in the e-diary, the event(s) should be recorded on the AE page of the CRF, regardless of whether the investigator considers the event(s) to be clinically significant.

Investigators (or appropriately qualified designee) are required to review the e-diary data online to evaluate subject compliance and as part of the ongoing safety review (see Stopping Rules in [Section 7.4](#)).

The investigator or designee must obtain stop dates for any reactions ongoing on the last day that the e-diary was completed. The stop dates should be documented in the source documents and the information entered in the CRF.

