6.1.1.2. Additional Summary for Assessing Local Reactions

To support the assessment of local reactions, similar endpoints will be summarized for the Primary Study Cohort - Stage 2 within 14 days after Vaccination 2; as well as for the RSV Vaccine Month-0, Month-2 Cohort within 14 days after Vaccination 1 and within 14 days after Vaccination 2.

To support the assessment of local reactions, additional endpoints (as defined in [Section 3.1.1](#)) will be summarized with all analysis time points (within 14 days after Vaccination 1 and within 14 days after Vaccination 2), analysis populations (Primary Study Cohort - Stage 1, Primary Study Cohort - Stage 2, and RSV Vaccine Month-0, Month-2 Cohort), analysis methodology, and appropriate reporting results. Confirmed e-diary errors will be excluded from these analyses.

CCI

PFIZER CONFIDENTIAL

Binary Endpoints

The percentage (%), the numerator (n) and denominator (N) used in the percentage calculation, and the corresponding 95% Clopper-Pearson CI will be presented for each vaccine group after each vaccination for the following endpoints:

- Subjects reporting any severe local reaction on each day and any day (Day 1 through Day 14).

Continuous Endpoints

The following endpoints will be summarized by displaying n, mean, median, standard deviation, minimum, and maximum for each vaccine group:

- Duration of each local reaction after vaccination.
- Onset day of each local reaction after vaccination.
- Onset day of any local reaction after vaccination.

Figures: Bar charts with the proportions of subjects reporting each local reaction within 14 days after vaccination will be plotted for each vaccine group. The bars will be stacked by maximum severity to highlight the proportions of subjects by severity.

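### Reactions whose stop date is never obtained, or that become chronic, have duration set to missing; this can understate mean and maximum duration in the supportive summaries

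*SAP*

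**What the plan says.** SAP 3.1.1.3 defines duration as resolution date minus start date plus one day. The resolution date has two possible sources. One is the last diary day on which the reaction is recorded. The other is the date the reaction ends, "if it is unresolved during the subject diary recording period (end date collected on the case report form [CRF]), unless chronicity is established". If neither source gives a date, the rule is: "If there is no known end date, the duration will be considered unknown and set to “missing".

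SAP 3.1.2 extends this to systemic events: "The derivations below for systemic events will be handled similarly to the way local reactions are handled". SAP 5.3.1 refers missing safety data back to the endpoint sections, so no other rule applies.

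Duration is reported under the additional summaries in SAP 6.1.1.2 and 6.1.2.2. For local reactions the wording is: "The following endpoints will be summarized by displaying n, mean, median, standard deviation, minimum, and maximum for each vaccine group".

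On the collection side, Protocol 7.3.1 states: "The investigator or designee must obtain stop dates for any reactions ongoing on the last day that the e-diary was completed". It continues: "The stop dates should be documented in the source documents and the information entered in the CRF". The 1-month visits (Protocol 6.1.3, 6.2.3, 6.3.3 and 6.3.6) carry the step: "Collect stop dates of any e-diary events ongoing on the last day that the e-diary was completed and record stop dates in the CRF".

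**The concern.** A reaction that stops within the diary has an end date by definition, so the missing rule can fall only on reactions that had not resolved when last observed. Whether a duration is missing therefore depends on how long the reaction lasts. The rule also discards information already collected, because the diary gives a start date and a last day on which the reaction was present.

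The clause on chronicity adds a second gap. It exempts chronic reactions from the end-date definition but puts nothing in its place, so the most persistent reactions may have no defined duration.

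At stake are the mean and maximum duration per vaccine group. Duration describes tolerability alongside the primary objective, and with about 31 subjects per group (Protocol Table 4) one omitted reaction can change both figures.

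**Working it through.** The plan gives no figure for duration, unresolved reactions or missing stop dates, so there is nothing to reproduce. The check is a reading of the rule followed by arithmetic on assumed data.

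**Step 1: who can have a missing duration (SAP 3.1.1.3 with Protocol 7.3.1)**

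| Reaction | End date from | Duration |
|---|---|---|
| Ends within the diary | Last diary day recorded | Complete |
| Ongoing at last diary entry, stop date obtained | CRF | Complete, may run past Day 14 |
| Ongoing at last diary entry, stop date not obtained | None | Missing |
| Chronicity established | None defined | Missing, on a natural reading |

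Only the last two rows lose their duration. Subjects who withdraw because of diary events (foreseen in Protocol 7.3.1) or are lost to follow-up (Protocol 6.5) are the likeliest source of the third row.

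**Step 2: size when the only persistent reaction has no stop date (assumed)**

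Take 15 reactors, with resolved reactions averaging 2.5 days. An unresolved reaction starts on Day 1 and is still present on Day 14, so its known minimum is 14 − 1 + 1 = 14 days.

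- One such case: the rule reports 2.5 days from n = 14. The mean is at least (14 × 2.5 + 14)/15 = 3.27, a ratio of 1.31. The maximum is at least 14 days but does not appear.
- Two such cases: the mean is at least (13 × 2.5 + 2 × 14)/15 = 4.03, a ratio of 1.61.
- One case whose diary stopped on Day 3: the known minimum is at most 3 days, giving (14 × 2.5 + 3)/15 = 2.53, a ratio of 1.01.

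**Step 3: size when some stop dates are obtained (assumed)**

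Take 20 reactors: 18 resolved at a mean of 3 days, and two ongoing at diary end that truly last 16 to 30 days.

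- Both stop dates obtained: (54 + 2 × 16)/20 = 4.30 to (54 + 2 × 30)/20 = 5.70. Nothing is understated.
- One stop date missing, current rule: (54 + 16)/19 = 3.68 to (54 + 30)/19 = 4.42, which is 14% to 22% below the true mean.
- One stop date missing, 14-day minimum kept: (54 + 16 + 14)/20 = 4.20 to (54 + 30 + 14)/20 = 4.90. This is closer, and still a lower bound.

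**Step 4: median**

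Dropping the largest of 15 values moves the median from the 8th ordered value to the midpoint of the 7th and 8th. Dropping two moves it to the 7th. Either shift is normally small.

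**The case against.** The strongest objection is that the plan already deals with reactions that outlast the diary. A reader might infer from the missing rule that every reaction ongoing on Day 14 leaves the summaries. The documents do not support that: SAP 3.1.1.3 takes the end date from the CRF, and the protocol makes collecting it mandatory and schedules it at the 1-month visits. Protocol 7.3.3 and 7.3.4 add reporting of events that persist past the diary, and 7.3.5 requires daily temperatures until a Day 14 fever resolves. If every stop date is obtained and no reaction becomes chronic, the bias is zero. This part of the objection stands and confines the point to the residual cases.

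Three further arguments stand in part:

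- An unresolved reaction need not be long. If the diary stopped early, the known minimum is short, and dropping a reaction that was truly short could even raise the mean. The effect is therefore that duration can be understated, not that it must be.
- Each duration summary shows n, so a reader can compare it with the number reporting the reaction. That reveals how many durations are missing, but not that they belong to unresolved reactions or how long those had already lasted.
- Duration is a supportive, descriptive summary. The primary reactogenicity analysis (SAP 6.1.1.1 and 6.1.2.1) is the proportion of subjects by maximum severity, which does not use the end date. No section names duration as a criterion for choosing a formulation.

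The duty to collect stop dates does not settle the matter. The SAP provides for unknown end dates, so it expects some, and the question is how best to handle them.

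**Conclusion.** The point holds in a narrow form and is minor. Reactions with no obtainable stop date, and probably chronic ones, lose their duration although a minimum is known. Because they were unresolved at last observation, leaving them out can understate the mean and maximum duration for local reactions and systemic events.

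The size cannot be taken from the documents. Under the assumed figures, the known-minimum mean exceeds the reported mean by between 1% (one case, diary stopped on Day 3) and 61% (two of 15 reactors still affected on Day 14). These rest on one or two residual cases in a small group; the actual number is unknown and probably small.

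The tempting larger conclusions, that the primary reactogenicity results or the choice of formulation are compromised, do not follow. Affected subjects stay in the presence and maximum-severity tables, and all analyses are descriptive without decision rules (SAP 5.1.2).

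**What to change.** In SAP 3.1.1.3, and by reference in 3.1.2, replace the missing rule along these lines: where no end date is known, or chronicity is established, duration is the last day known ongoing minus the start date plus 1, flagged as censored. The existing limit, that a reaction is not carried past the next vaccination, continues to apply.

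In SAP 6.1.1.2 and 6.1.2.2:

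- report the number of flagged durations per vaccine group;
- print the maximum with ≥ when it is a flagged value;
- footnote the mean as a lower bound whenever any duration is flagged.

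A Kaplan-Meier median is optional; with so few censored values expected, it would add little.

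The cost is SAP wording, one derivation flag and slightly heavier footnoting. No new data are needed.
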